## Power Analysis and Sample Size

We expect an approximate drop-out rate of 25% based on our current more burdensome protocol within a sample of 18-40 year-old females. Therefore, we will enroll a total of 125 female and 125 male participants to ensure we have 100 per sex group to complete the 4 week follow-up for the primary outcome. Participants will be randomized 1:1 to PRO or placebo, separately by sex group, as described above. In our earlier work ([name] et al, 2008), the luteal quit group had a prevalence of 66% relapse at 30 days; this estimates the placebo group relapse rate for our proposed study. Based on a two-tailed Pearson chi-square test with alpha=0.025 for each sex group, a sample size of 100 completers per sex group will have 80% power to detect an odds ratio of 3.5 or higher for comparing smoking relapse prevalence in the placebo group to smoking relapse prevalence in the PRO group. We observed an odds ratio of 3.2 for follicular quit group relapse compared to luteal quit group relapse ([name] et al, 2008). Since our PRO group will receive substantially more progesterone than during the typical natural female cycle, it is reasonable to expect a slightly larger odds ratio for PRO compared to placebo. Since the difference in progesterone levels between the male PRO group and the male PBO group will be larger than the difference between the female PRO group and the female PBO group, we expect a larger odds ratio (hence higher power) for the male treatment comparison.

## B. TRIAL MANAGEMENT

### Enrolling Clinics and Data Collection

**Centers.** All study subject enrollment and data collection will be done at the Delaware Clinical Research Unit at the University of Minnesota.

**Projected Timetable.** The projected timetable is displayed in Table 1.

**Table 1. Project Timeline**

	Year 1				Year 2				Year 3				Year 4				Year 5			
	Q1	Q2	Q3	Q4																
Training Staff and Study Preparation	X	X																		
Participant Recruitment		X	X	X	X	X	X	X	X	X	X	X	X	X	X	X	X	X	X	
Participant Follow-up			X	X	X	X	X	X	X	X	X	X	X	X	X	X	X	X	X	X
Data Entry and Cleaning			X	X	X	X	X	X	X	X	X	X	X	X	X	X	X	X	X	X
Analysis and Report Writing																	X	X	X	X

**Target Population Distribution.** This study will be recruiting both men (n=100) and women (n=100) because the research question addressed is designed to assess sex differences. Specifically, the effects of a female sex hormone (progesterone) on smoking cessation in men and women who are motivated to quit smoking will be examined. Study participants will be recruited from the greater metropolitan area of Minneapolis and St. Paul, via mass media advertisements. Estimates indicate that as of 2009 the Minneapolis and St. Paul, Minnesota Twin Cities metro area included approximately 50.5% female and 20.2% of the population in the racial minority groups (Black= 11.0%, Asian = 5.8%, American Indian = 1.2%, other = 4.0%) and the Hispanic population is 6.4%. In the absence of minority population response to advertisements, additional targeted strategies will be implemented to solicit their participation. These efforts are effective; for example, our current study has been successful in recruiting a diverse sample: 49% are White, 33% are Black, 8% are more than one race and 10% are other.

## Enrollment Table

Study Title: Progesterone, Impulsivity and Smoking Cessation

Total Planned Enrollment: 250

TARGETED/PLANNED ENROLLMENT: Number of Subjects			
Ethnic Category	Females	Males	Total
Hispanic or Latino	4	4	8
Not Hispanic or Latino	121	121	242
Ethnic Category: Total of All Subjects *	125	125	250
Racial Categories			
American Indian/Alaska Native	4	4	8
Asian	4	4	8
Native Hawaiian or Other Pacific Islander	1	1	2
Black or African American	15	15	30
White	101	101	202
Racial Categories: Total of All Subjects *	125	125	250

\* The "Ethnic Category: Total of All Subjects" must be equal to the "Racial Categories: Total of All Subjects."

## C. DATA MANAGEMENT AND ANALYSIS

**Data Acquisition and Transmission.** Data collection at study visits will take the form of subjective measures (forms), blood and urine samples, and will be identified with a three-digit identification number. Samples will be collected and stored with the subject ID code only. The coordinator will keep the code that links the subject ID with the identity of the subject in a database protected by two-levels of security stored it separately from the data.

**Data Entry Methods.** All self-report data collection items throughout the study will be self-administered per direction of study staff via a computer program (REDCap; <http://project-redcap.org/>) to improve the quality of data (by avoiding missing data, illegible data, etc) and limit the time spent on data entry and cleaning. Any data not entered directly into a computer system (i.e. height, weight, blood pressure) will be double entered on our password protected server by trained data entry personnel at the Tobacco Research Programs using the Access data entry programs. The study coordinator will be available to monitor the data and correct any discrepancies based on source documents.

**Data Analysis Plan.** Addressing Hypothesis 1: Our primary outcome is the binary indicator of relapsed yes/no at the week 4 visit. An unadjusted assessment of the treatment effect will come from a logistic regression of this binary outcome on randomized treatment assignment, separately by sex. The sex-specific treatment effect will be considered statistically significant if the p-value is <0.025. All persons randomized and with a measured primary outcome at the week 4 visit will be included in this analysis, regardless of whether or not they ever took any of their assigned treatment (intent-to-treat analysis); persons with missed visits are discussed below. While we expect baseline covariates to be balanced across treatment groups due to the randomization, an adjusted assessment of the treatment effect will then be carried out by a logistic regression including the randomized treatment assignment and pre-specified adjusting covariates such as age, baseline progesterone, estradiol, baseline impulsivity measures, etc. This pre-specified list will be determined by the study team during the finalization of the protocol, prior to the first study enrollment. We expect these analyses to be somewhat conservative, since they do not explicitly account for the randomized permuted blocking (Matts and Lachin, 1988). An analysis that accounts for the blocking (such as a stratified Mantel-Haenzel test) cannot be generalized to include the adjustment for impulsivity measures, for example, which are a focus of this proposal.

Hypotheses:

Hypothesis 1: For both males and females, a lower proportion of subjects randomized to PRO will relapse by 4 weeks after quit date compared to those randomized to PBO.

Hypothesis 2: For both males and females, subjects randomized to PRO will have more days to relapse compared to those randomized to PBO.

Hypothesis 3: There will be a sex difference in smoking relapse such that females, regardless of randomization assignment, will have fewer days to relapse compared to males.

Hypothesis 4: Impulsivity will be a stronger relapse predictor in females than males.

Hypothesis 5: Among those with higher levels of serum PRO the influence of impulsivity on smoking relapse will be damped.

Addressing Hypothesis 2: Our secondary outcomes include the binary indicator of relapsed yes/no at the week 12 visit, and days to relapse, as described above. The binary outcome will be analyzed as described for the primary outcome. Days to relapse will be analyzed using Kaplan-Meier survival curves with a log-rank test comparing treatments (unadjusted) and Cox proportional hazards analysis (adjusted for other characteristics), both of which allow for loss-to-follow up via right censoring (Therneau and Grambsch, 2000), separately for the CA and PA definitions. Adjusting variables will be selected as described for the primary outcome. The proportional hazards assumption on the treatment effect will be examined and tested (Lin, Wei, and Ying, 1993; Grambsch and Therneau, 1994).

To address Hypothesis 3, we will pool the male and female data and test for an interaction between sex and treatment assignment in an adjusted Cox regression for the days to relapse outcomes. To address Hypothesis 4, we will test a baseline impulsivity by sex interaction in the logistic regressions for the binary outcomes and in the Cox regressions for the days to relapse outcomes. To address Hypothesis 5, we will test a baseline impulsivity by baseline serum progesterone interaction in the logistic regressions for the binary outcomes and in the Cox regressions for the days to relapse outcomes. While this study was designed to be powered for Hypothesis 1, rather than for these comparisons, these will be used to generate preliminary data and hypotheses for future research on sex differences in addiction treatment and impulsivity.

#### **D. QUALITY ASSURANCE**

Data collected via computer programs (EMAs and REDCap) will be monitored by the study coordinator by random inspection of completed forms, and any problems detected will be discussed with the PI. The Statistics Core ([name], Director) will analyze the data using the SAS program. In addition, the Statistics Core will provide support in developing data entry programs. Data analyses will be completed at the end of the study. For missing data: Persons who do not attend a week 4 visit, assessment of the primary outcome is not directly possible. During their week 5, study staff will attempt to contact them in order to collect by phone and/or email a self-reported recall of smoking status as of week 4; outcomes collected in this way will be denoted separately in the study database. The primary outcome analysis will be carried out after excluding these subjects, including those for whom we were able to obtain a self-reported recall outcome, where we conservatively assumed all these individuals relapsed as of their week 4 visit. Since 'missing at random' is a strong statistical assumption to make in the primary outcome analysis, we will also carry out descriptive analyses to see whether persons missing their week 4 visit differed in their baseline characteristics or treatment assignment from persons not missing their week 4 visit.

#### **E. Regulatory Issues: Adverse Events, Serious Adverse Events, Collection and Reporting**

Adverse Events: An adverse event is any unwanted experience or event occurring during the course of a clinical trial. At each visit, either a research nurse or physician will query the participant and log side effects and other treatment emergent events since the past visit, recording their severity (mild, moderate, severe, life-threatening), what action was taken, and whether the symptoms are continuing or resolved. The study investigators will follow all AEs to the point of a satisfactory resolution. A study subject may be withdrawn from the study if the PI determines it is the best decision for protection of the safety of the subject. All AEs will be assessed to determine if they meet criteria for an SAE. AEs will be quantified separately by sex and treatment groups and compared across treatment groups with Fisher's exact test (for binary events) or with chi-square test (for counts of events or event rates). The event will be documented as to whether there is 1) no relationship between the study drug and the adverse event, 2) the adverse event is unlikely related to administration of the study drug, 3) the adverse event is possibly related to study drug administration, or 4) the adverse event is probably related to the administration of the study drug.

Serious Adverse Events (SAE): A serious adverse event is defined as an outcome that is 1) fatal or life-threatening, 2) significantly or permanently disabling or incapacitating, 3) requires or prolongs inpatient hospitalization, or 4) results in

a congenital anomaly. SAE's, whether or not related to study medication, will be reported to the IRB and NIDA. All drug related adverse events of a non-serious nature are reported to the University of Minnesota's IRB on a quarterly basis. Serious adverse events will be reported by telephone to the IRB, and to NIDA and the FDA within the three days of our receipt of information regarding the event and written reports will be submitted within ten days. If a subject either withdraws from the study or the investigator decides to discontinue a subject due to SAE, the subject will have appropriate follow-up medical monitoring. Monitoring will continue until the problem requiring hospitalization was resolved or stabilized with no further change expected, is clearly unrelated to study medication, or results in death. Outcome of SAEs will be periodically reported to NIDA. A summary of the SAEs that occurred during the previous year will be included in the annual progress report to NIDA. Finally, the PI's will ensure that serious adverse events reported to NIDA via the serious adverse event tracking and reporting system at <https://saetrs.nida.nih.gov/>.

The Principal Investigator will then take appropriate action (including study modification) as agreed upon by these monitoring groups including the DSMB when needed. The Principal Investigator will determine whether the seriousness of the event warrants removal of the participant from the study. Appropriate diagnostic and therapeutic interventions will be initiated and the participant will be medically followed and kept under observation as long as medically indicated. After the review of the data, the DSMB report will make recommendations about whether the trial should continue with or without modifications, or be terminated. Any potential conflict of interest in the Data and Safety Monitoring Board will be disclosed.

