**Table 1. Timing of Study Procedures by Sex**

	Female Subjects	Male Subjects
Initial Phone Interview		Anytime
Screening Visit 1	Menstrual Cycle Days 1-7	Within 2 weeks of Phone Screen
Screening Visit 2		Within 3 days of Screening Visit 1
Baseline Visit	Within 3 days after LH Surge	Delay matched to Female Subject
Medication Start		8PM on day of Baseline Visit
Quit Date		7 days after Baseline Visit
Week 0		Day of Quit Date
Week 1-Week 11		Weekly
Medication End		Day of Week 11 Visit
Final Visit		12 Weeks after Quit Date

Weeks 0-12 (Visits 4-16): The Week 0 clinic visit will occur on the assigned quit date. Subjects will attend clinic visits on a weekly basis thereafter for twelve weeks. At weeks 0-4, week 8 and week 12 blood samples (hormone measurement) will be collected. Urine samples will be collected at all visits from all participants (pregnancy tests for females; and visual inspection of urine color to confirm compliance with taking study medication via riboflavin filler). At weeks 0-4, week 8 and week 12 urine will be saved for biochemical confirmation of smoking status via nicotine/cotinine levels. Subjects will also complete several forms and questionnaires (described below). Subjects will also return the medication bottle and unused medication, be given a new two-week supply and adverse events will be assessed. At Week 11, study medication will be discontinued. Finally, subjects will receive brief smoking cessation behavioral counseling (Appendix A). At the end of each visit subjects will be paid for their time. These visits will take approximately 30-45 minutes to complete.

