Study Adherence: To encourage compliance the following will occur: (1) at the Baseline Visit, subjects will be given a schedule of all remaining appointments; (2) at each visit the subjects will be given an appointment reminder card for the next visit; (3) reminder calls, texts and/or emails (per subject's preference) will be placed or sent the day before each visit; (4) subjects will be routinely reminded that regardless of their smoking status their data are valuable and important; and (5) regardless of smoking status, subjects will be compensated at each visit (described in the following). If a subject misses a visit, study staff will try to reach him/her by phone that day to reschedule for one to three days later. If that does not work, staff will contact the subject's designated 'contact person' (i.e., someone who does not live with the subject but knows how to get in touch). If a subject does not attend any visits after the screening visits, he/she will be labeled as a "drop" and replaced. If the subject discontinues from the study after randomization but before the final follow-up visit, he/she will be labeled an "*incomplete*" but not replaced. If a subject does not quit on their assigned quit date or relapses later, she/he will be encouraged to stay in the study and make another quit attempt; such that we will follow them for three months regardless of smoking status. Subjects who complete the four week follow-up period after quit date, regardless of smoking status, will be labeled a "*completer*" for the primary outcome and not replaced. Our sample size goal to sufficiently power the primary outcome is for 200 completers.

[figure not shown]

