#### **B.4.5. Study Medication**

Subjects will be stratified by sex and then randomly assigned to PRO or PBO, as described above. All medication (active and placebo) will be prepared by the University of Minnesota Clinical Trials Research Pharmacy, which is a specialized facility that prepares medication clinical trials including our ongoing research. The research pharmacist ([name] Pharm D) will provide medications. There is oversight and monitoring with regular audits by local regulatory boards including the IRB. This study requires double-blind procedures, therefore progesterone will be over encapsulated and be identical to the placebo capsules. To prevent against the possibility of missed medication in the event of a missed clinic visits, subjects will receive a two week supply (to ensure no medication is missed in the event of an unexpected miss clinic visit due to illness or transportation issues, for example) of study medication from study staff at each clinic visit beginning with the Baseline Visit. Medications will be discontinued at the Week 11 clinic visit.

**Progesterone:** The progesterone will be given in the form of an active or placebo micronized natural progesterone (generic Prometrium). All subjects will take 200 mg twice daily (approximately 8am and 8pm) for twelve weeks starting seven days prior to the assigned quit date. The dosage was selected to ensure that serum progesterone levels will be consistent with those observed in the natural Luteal phase of the menstrual cycle

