- **Perceived Stress Scale** (PSS; Roberti et al, 2006): This ten item questionnaire will measure perceived stress. The items are rated on a 5-point scale, ranging from 0 (never) to 4 (very often), and they focus on events during the last week. The scale has adequate reliability and validity. This item will only be completed once during the screening process. This item will be completed at Screening Visit 1. This item will be completed at each clinic visit thereafter.
- **Life Event Occurrence Survey** (LEOS; McKee et al, 2005): This item will assess and account for the presence of current or recent significant life events. This measure includes 38 yes/no questions assessing various events that may have happened in the last six months including aspects of work, social life, family and finances. The measure includes instructions on how to rate the level of disruption the event caused in the subjects life from none too severe disruption. This measure will be administered at screening visit 1 and the final visit W12.
- **Columbia-Suicide Severity Rating Scale:** This questionnaire (C-SSRS; Posner et al, 2009) will be completed at each clinic visit to assess suicidal ideation, given this is listed as an SAE on the Prometrium label. If any item of suicidality is endorsed referrals to the appropriate mental health care will be made.
- **Sociodemographic Variables:** At the first screening visit we will collect information on age, race/ethnicity, education, income and other related variables. This item will be completed at Screening Visit 1 only.
- **Serum Estradiol:** At Screening Visit 1 and clinic visits 0-4, 8 and 12, blood samples will be collected to allow for the measurement of serum estradiol. Following identical procedures described above for serum progesterone, approximately two mL of serum will be analyzed by HealthEast Medical Laboratories using chemiluminescence.
- **Leisure Time Exercise Questionnaire** (LTEQ): This questionnaire has four-items to assess strenuous, moderate and mild exercise completed during leisure time and has high reliability ( $r=0.83, 0.85$ ; Gordin & Shepard, 1985).
- **Caffeine Use:** Caffeine use will be collected via self-report at each clinic visit using the TimeLine FollowBack methods in which participants will report the total number of ounces of caffeinated beverages drank per day for each day.

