Handling missing outcomes: For persons who do not attend a week 4 visit, assessment of the primary outcome is not directly possible. During their week 5, study staff will attempt to contact them in order to collect by phone and/or email a self-reported recall of smoking status as of week 4; outcomes collected in this way will be denoted separately in the study database. The primary outcome analysis will be carried out once excluding these persons, once including those for whom we were able to obtain a self-reported recall outcome, and once where we conservatively assume all these persons relapsed as of their week 4 visit. Since 'missing at random' is a strong statistical assumption to make in the primary outcome analysis, we will also carry out descriptive analyses to see whether persons missing their week 4 visit differed in their baseline characteristics or treatment assignment from persons not missing their week 4 visit.

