A Baseline Visit will occur seven days prior to the subjects assigned quit date. Females will have their assigned quit date set seven to nine days after ovulation. Ovulation will be determined through the use of urine ovulation tests that female subjects will use daily for ten days in a row. Males will have their assigned quit date matched to a female subject for a similar delay and procedure completion. At this visit subjects' weight, blood pressure, heart rate, and carbon monoxide level will be measured. They will also provide urine and blood samples (20cc) for later measurement of nicotine exposure (specifically nicotine and cotinine) and hormone levels (specifically progesterone and estradiol), respectively. At this visit subjects will receive their study medication and be provided regimen/administration instructions. They will also receive brief smoking cessation behavioral counseling, be compensated for their time, and receive a schedule of all follow-up visits.

At the follow-up visits (weekly visits, Week 0 - Week 12) all subjects will have their weight, blood pressure, heart rate and expired carbon monoxide measured. The subjects will provide urine (nicotine, cotinine) at all visits and blood (progesterone, estradiol) samples at visits 0-4, 8 and 12 and complete several forms to measure smoking-related symptomatology, mood, and related items. The study nurse will assess their adverse events. At the end of each visit subjects will receive additional behavioral counseling, additional study medication and be compensated for their time.

Subjects could earn up to \$480 for their study participation (\$25 for screening visit x 2 screening visits + \$20 for baseline visit + \$20 for follow-up clinic visits x 13 visits + \$75 bonus for missing less than three visits + \$75 for completing the study).

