Generic Prometrium, a natural progesterone, is generally well tolerated. The most common adverse effect is sedation. Other less common adverse effects include menstrual irregularity, spotting or breakthrough bleeding, dizziness, cramps, nausea, fatigue, headache and breast tenderness (de Lignieres, 1999; Simon, 1995, Sofuglu, 2009). Other side effects attributed to synthetic progesterone, including depression, fluid retention, pruritus, jaundice, rash and thrombotic disorders, are unlikely to occur. Recently there have been reports of increased risk of stroke, coronary artery disease, venous thromboembolism and breast cancer in postmenopausal females who have been on long-term hormone replacement treatment with estradiol and progestin (medroxyprogesterone) combination (Anonymous, 2002; Grady et al., 2002; Hulley et al., 2002; Nelson et al., 2002). While some of these adverse events develop after years of treatment, venous thromboembolism is seen within the first year of treatment (Anonymous, 2002). It is possible that progestins may contribute to thromboembolism seen during estradiol and progestin treatment and thromboembolism is listed in the PDR as one of the adverse events for medroxyprogesterone treatment (PDR, 2002). In contrast to synthetic progestins, natural progesterone is not known to cause thromboembolism (PDR, 2002). However, as a safety measure for these serious adverse events, we will exclude subjects with history of thrombophlebitis, deep vein thrombosis, pulmonary embolus, clotting or bleeding disorders, heart disease, diabetes or history of stroke. Possible adverse events from generic Prometrium will be assessed weekly by the research nurse ([name], NP) in consultation with the study physicians ([name] MD, [name] MD). If the side effects cannot be tolerated the medication dosage will be decreased to 200 mg daily.

Although uncomfortable, withdrawal symptoms do not pose significant health risks. Subjects who participate in this study will be asked to quit smoking on an assigned quit date. The smoking abstinence may result in increased irritability, anxiety, tension, depression, increased hunger or drowsiness.

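### New adverse events after the last attended visit have no planned collection in participants who stop attending; a few questions added to existing contacts would largely close the gap

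*Combined protocol and SAP*

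**What the plan says.** **Scheduled AE collection is at visits.** Section E of the Data Safety and Monitoring Plan (DSMP) says that at each visit a research nurse or physician "will query the participant and log side effects and other treatment emergent events since the past visit". Protocol B.4.3 (Weeks 0-12) lists what happens at a clinic visit, including that participants "be given a new two-week supply and adverse events will be assessed". The DSMP's Screening and Visit Procedures says of the follow-up visits: "The study nurse will assess their adverse events". DSMP section F gives a frequency without naming a visit: "Possible adverse events from generic Prometrium will be assessed weekly by the research nurse". The suicidality scale in B.4.6 "will be completed at each clinic visit to assess suicidal ideation", and the depression inventory is also completed at clinic visits.

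**Contacts with someone who does not attend.**
- B.4.3 (Study Adherence): after a missed visit, "study staff will try to reach him/her by phone that day to reschedule for one to three days later". If that fails, staff turn to the designated contact person.
- B.4.8 (Handling missing outcomes), repeated in DSMP section D: if Week 4 was missed, then during Week 5 "study staff will attempt to contact them in order to collect by phone and/or email a self-reported recall of smoking status".
- B.4.6: a debriefing questionnaire at the end of participation or Week 12, whichever is later, asks which treatment the participant thinks was given.

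**Drug in hand.** B.4.5 says that "subjects will receive a two week supply" at each clinic visit from Baseline, so that a missed visit does not interrupt dosing.

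**Use of the data.** B.4.8 (Safety analyses) and DSMP section E tabulate AEs by sex and treatment and compare the arms with Fisher's exact or chi-square tests.

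**The concern.** Someone who stops attending can go on taking capsules after the last AE query, and no later contact has the stated job of asking about them. For a person who never returns after Baseline, the unqueried time includes the first week of dosing, the period for which DSMP section F takes a specific precaution against sedation.

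This matters because the arms are formally compared on AEs, drop-out of about 25% is expected before the Week 4 outcome, and B.4.5 describes earlier use of the drug as lasting under a month, against twelve weeks here. If some people leave because of a side effect, and this happens more in one arm, the recorded difference between arms is distorted. For smoking status, the plan itself doubts that missing data are missing at random, adds an outreach contact and runs three analyses. AEs get no counterpart.

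**Working it through.** **Step 1. Does any provision ask a non-attender about new AEs?**

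| Provision | What it covers | New AEs after the last visit? |
|---|---|---|
| Query at each visit (B.4.3; DSMP Screening and Visit Procedures; DSMP E) | Interval since the previous visit | Only if the person returns |
| Weekly assessment (DSMP F) | Most naturally the weekly visits | Not stated |
| Missed-visit call and contact person (B.4.3) | Rescheduling; reaching the participant | Not stated |
| Week 5 contact (B.4.8; DSMP D) | Smoking status at Week 4 | Not stated |
| Debriefing questionnaire (B.4.6) | Guessed assignment | Not stated |
| Follow-up of AEs to resolution (DSMP E) | AEs already logged | No |
| Follow-up after withdrawal or SAE discontinuation (DSMP E) | Medical monitoring, ending when the hospitalized problem settles | No query specified |
| 24-hour telephone line (DSMP F) | Calls the participant makes | Only if volunteered |
| Medical supervision, close and daily monitoring (DSMP F, H) | General promises | No procedure given |

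**Step 2. How much dosing could go unqueried?** The plan gives no figure for this, so there is none to reproduce.
- Planned dosing: Baseline (7 days before quit date) to Week 11 is 7 + 77 = 84 days; 250 × 84 = 21,000 participant-days.
- Expected losses by Week 4: 250 − 200 = 50, or 25% of 250 = 62.5, taken as 62.
- Unqueried at most: 50 × 14 = 700 and 62 × 14 = 868 days, if every loss had received drug, never returned and took the whole supply.
- Against planned dosing: 700 / 21,000 = 3.3%; 868 / 21,000 = 4.1%.
- Against dosing that would occur if all were lost straight after Baseline: 700 / (200 × 84 + 700) = 700 / 17,500 = 4.0%; 868 / (188 × 84 + 868) = 868 / 16,660 = 5.2%.
- If only half the losses fit that description (assumed): 25 × 14 = 350 and 31 × 14 = 434 days, 1.7% and 2.1% of 21,000.

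Losses after Week 4 would add to these figures; the documents give no rate for them.

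**Step 3. What could this do to the between-arm comparison?** The documents give no AE rates, so this is illustration only. Take one sex, 62 per arm, and assume true rates of 30% on progesterone (PRO) and 15% on placebo: 18.6 and 9.3 people affected, a difference of 15 points and a ratio of 2.0. Recorded rate = true rate × (1 − share of affected people missed).

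| Affected people missed, PRO / placebo | How it could arise (assumed) | Recorded rates | Difference | Ratio |
|---|---|---|---|---|
| 12.5% / 12.5% | 25% loss in both arms, half of lost participants' AEs arising only after the last visit | 26.25% vs 13.13% | 13.1 points | 2.00 |
| 15% / 10% | Loss 30% vs 20%, same half | 25.5% vs 13.5% | 12.0 points | 1.89 |
| 10% / 15% | Loss 20% vs 30%, same half | 27.0% vs 12.75% | 14.3 points | 2.12 |
| 20% / 10% | Equal 25% loss (15.5 per arm), but a first AE only after the last visit in 24% of those lost on PRO and 6% on placebo | 24.0% vs 13.5% | 10.5 points | 1.78 |
| 10% / 20% | The missed shares reversed | 27.0% vs 12.0% | 15.0 points | 2.25 |

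For the fourth row, 20% of 18.6 is 3.7 people (3.7 / 15.5 = 24%) and 10% of 9.3 is 0.9 (0.9 / 15.5 = 6%). Across rows, about 1 to 4 people per arm are missed. The proportional change in the ratio does not depend on the assumed AE rates: it is (1 − share missed on PRO) / (1 − share missed on placebo), from 0.80 / 0.90 = 0.89 to 0.90 / 0.80 = 1.125.

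**The case against.** The best counter-argument is that this reads a lot into silence. DSMP section F promises weekly assessment without mentioning a visit. The definition of an AE in section E is not limited to visits, so a side effect mentioned on a rescheduling call could be logged. The follow-up promised in section E can be read as covering anyone who withdraws. A call script is operational detail, and staff may already ask. Dose reduction, reminders, visit payments and the 24-hour line all make silent loss less likely.

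Much of this stands, and it limits the weight of the point. It does not close the gap. The nurse's weekly assessment coincides with weekly visits, and no other weekly contact is described. Permission to log what is volunteered is different from asking.

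Two stronger readings are tempting. A reader might infer that AEs in people who drop out are lost altogether. They are not: events logged earlier still count and are followed up, and anyone who returns is asked about the interval. A reader might also infer that the gap hides harm from progesterone. The documents do not support a direction: they give no AE rates, no loss by arm and no reasons for leaving, and Step 3 moves the ratio either way. Nor is 3.3% to 4.1% an upper bound on the share of dosing, because its denominator counts drug that lost participants would never receive and its numerator omits losses after Week 4.

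**Conclusion.** The concern holds as a cheap improvement to data collection. As written, new AEs after the last attended visit in someone who does not return are recorded only if volunteered or learned of as serious events. Among the losses expected by Week 4, this leaves at most 700 to 868 participant-days unqueried. Those figures assume that every loss had been dosed and took all remaining drug. The true number is probably lower, since the DSMP's eligibility section counts the 250 as consented, so some losses may precede dosing, and some who miss Week 4 will return. The effect on the AE comparison is of unknown direction and probably modest; the primary smoking analysis is untouched.

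**What to change.** 1. **B.4.3 (Study Adherence).** At each missed-visit call, and whenever a participant gives notice of withdrawal, ask about side effects or hospital care since the last visit, date of last dose, and reason for stopping. The first two missed-visit calls fall about 7 and 14 days after the last visit and so span the supply. For those who withdraw, repeat the questions once the two-week supply would have run out.
2. **B.4.8 (Handling missing outcomes) and DSMP section D.** Add the same questions to the Week 5 contact as a back-up.
3. **DSMP section E.** Pass positive answers to the research nurse or physician for severity and relatedness, and flag these events as collected by phone or email.
4. **B.4.8 (Safety analyses) and DSMP section E.** Keep the planned tests. Report by arm and sex how many dosed participants had no final AE query.

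The cost is three questions on contacts mostly already attempted, one further call for those who withdraw, a little nurse or physician time and one table row. Sample size, visits and tests do not change. Recall by phone or email is weaker, reaching back about 6 weeks for someone lost after Baseline and reached only in Week 5. Some people will not be reached, which is why the unqueried count is reported.
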